9.12. ADHD Symptoms

Based on input from the TEV-50717 Tourettes Syndrome Scientific Advisory Board (SAB), which contains experts in the area of child psychiatric and in the attempt to identify possible symptoms consistent with ADHD symptomatology, the items below from C&A-GTS-QOL were chosen:

Item 11 – Difficulty concentrating;

Item 12 – Had problems with your memory;

Item 13 – Lost or misplaced important things;

Item 14 – Had difficulty finishing your tasks once you started them;

Item 20 – Felt fidgety ((Version: Age 6-12 Years) or Felt restless or fidgety (Version: Age 13-18 Years).

The item below from CDI-2 self version was chosen:

Item 22 – Schoolwork.

Summary statistics will be provided to the observed values and change from baseline for Parts I and III combined based safety analysis set. This analyses are only exploratory and for signal detection purpose.

9.13. Columbia-Suicide Severity Rating Scale (C-SSRS)

The C-SSRS children's since last visit (SLV) scale is administered per [Table 3](#). Patients will be placed into categories for suicidal ideation and for suicidal behavior based on their responses to various questions.

The suicidal ideation categories will be determined as follows by examining the response to the 5 questions under Suicidal Ideation.

This document is confidential.

Statistical Analysis Plan for Interventional Studies

Sponsor: Teva Branded Pharmaceutical Products R&D, Inc./Nuvelution TS Pharma, INC.
 Protocol No.: TV50717-CNS-30047

Type	Section
Suicidal ideation	
(0) None – if response is No to Questions 1 and 2
 
(1) Wish to be Dead – if response to Question 1 is Yes and responses to Questions 2-5 are No.
 
(2) Non-Specific Active Suicidal Thoughts – if response to Question 2 is Yes and response to Questions 3-5 are No.
 
(3) Active Suicidal Ideation with Any Methods (Not Plan) without Intent to Act – if response to question 3 is Yes and response to questions 4 and 5 are No.
 
(4) Active Suicidal Ideation with Some Intent to Act, without Specific Plan – if response to Question 4 is Yes and response to Question 5 is No.
 
(5) Active Suicidal Ideation with Specific Plan and Intent – if response to Question 5 is Yes.

For suicidal behavior, the following categories will be used. The categories will be determined based on the response to the questions under suicidal behavior.

Type	Section
Suicidal behavior	
(6) Preparatory Acts or Behavior – if response to Preparatory Acts and Behavior is Yes and responses to Actual Attempt, Interrupted Attempt, Aborted Attempt, and Completed Suicide are No
 
(7) Aborted Attempt – if response to Aborted Attempt is Yes and responses to Actual Attempt, Aborted Attempt, and Completed Suicide are No.
 
(8) Interrupted Attempt – if response to Interrupted Attempt is Yes and response to Aborted Attempt, and Completed Suicide are No.
 
(9) Actual Attempt – if response to Actual Attempt is Yes and Completed Suicide is No.
 
(10) Completed Suicide - if response to Completed Suicide is Yes
 
(0) None – if responses to all the above 4 questions are No.

Suicidal ideation or behavior will be derived as the highest suicidal ideation or behavior score at the visit. Score of 0 represent “No Suicidal Ideation/Behavior”.

The frequency and percentage of suicidal ideation, suicidal behavior, suicidal ideation or behavior, and self-injurious behavior without suicidal intent from SLV version will be summarized by visit. Separate summaries will be prepared for the Parts I and III combined for all patients based on the Safety Analysis Set, and Part II by treatment group for the RWSAF Population.

Frequency and severity of suicidal ideation or behavior will also be summarized, using a shift table to examine changes in above C-SSRS scores from baseline compared to the worst (highest) category in the Parts I and III combined and Week 28 to Week 30 visit for Part II.

This document is confidential.

10. Interim Analyses

One interim analysis for Part I data is planned after 100 patients completed Part I. No blinded data from Part II will be included in the interim analysis, and hence, no alpha adjustment is needed for the analysis of the key efficacy endpoint in Part II.

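### The C-SSRS behavior rules in SAP section 9.13 make the aborted-attempt category impossible to assign and exclude the wrong item for interrupted attempts

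*SAP*

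**What the plan says.** SAP section 9.13 ranks suicidal behavior from 6 (preparatory acts) through 7 (aborted), 8 (interrupted) and 9 (actual attempt) to 10 (completed suicide), with 0 for none. Each category has its own rule:

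- Category 6: preparatory acts Yes, and "responses to Actual Attempt, Interrupted Attempt, Aborted Attempt, and Completed Suicide are No".
- Category 7: "if response to Aborted Attempt is Yes and responses to Actual Attempt, Aborted Attempt, and Completed Suicide are No".
- Category 8: "if response to Interrupted Attempt is Yes and response to Aborted Attempt, and Completed Suicide are No".
- Category 9: "if response to Actual Attempt is Yes and Completed Suicide is No".
- Category 10: "if response to Completed Suicide is Yes".
- Category 0: "if responses to all the above 4 questions are No".

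A combined variable follows: "Suicidal ideation or behavior will be derived as the highest suicidal ideation or behavior score at the visit". The scores are then tabulated by visit ("The frequency and percentage of suicidal ideation, suicidal behavior, suicidal ideation or behavior, and self-injurious behavior without suicidal intent from SLV version") and used in shift tables, which for Parts I and III compare baseline with the worst category reached.

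**The concern.** The rules for categories 6, 9 and 10 share one logic: the item itself is Yes and every higher-ranked item is No. Categories 7 and 8 break it. Category 7 excludes the very item it is meant to capture. Category 8 excludes the item ranked below it and leaves out Actual Attempt, which ranks above it. The rule for None speaks of four questions where five items are listed.

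The error runs in the unsafe direction. A child whose worst behavior is an aborted attempt gets no behavior category. If that child also had an interrupted attempt, it is lost too, because category 8 requires Aborted Attempt to be No.

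Safety is the study's primary objective (section 3.1). C-SSRS is a named safety endpoint for Parts I and III and for Part II (section 4.1), and it is in the interim analysis (section 10.1), which section 2.2 says is meant to support regulatory filings. In Part II the C-SSRS results are shown by treatment group, where such events are likely to be few and one lost case could change the picture.

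**Working it through.** There is no stated figure to reproduce; the check is whether the rules give each set of answers exactly one category.

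**Inputs.** The six rules of section 9.13, applied to five Yes/No items: Preparatory (P), Aborted (Ab), Interrupted (I), Actual (Ac), Completed (C). There are 2^5 = 32 patterns. The None rule is read as all five items No.

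**Rules as written.**

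| Category | Condition as written | Patterns meeting it |
|---|---|---|
| 0 | all five No | 1 |
| 6 | P Yes; Ab, I, Ac, C No | 1 |
| 7 | Ab Yes; Ac, Ab, C No | 0 |
| 8 | I Yes; Ab, C No (Ac and P free) | 2 × 2 = 4 |
| 9 | Ac Yes; C No (P, Ab, I free) | 2 × 2 × 2 = 8 |
| 10 | C Yes (other four free) | 2^4 = 16 |

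The conditions are met 1 + 1 + 0 + 4 + 8 + 16 = 30 times.

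**Patterns meeting two rules.** Categories 8 and 9 overlap when I and Ac are Yes and Ab and C are No. P is free, which gives 2 patterns. The number of distinct patterns classified is 30 − 2 = 28.

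**Patterns meeting no rule.** 32 − 28 = 4. These are Ab Yes, Ac No, C No, with P and I free (2 × 2 = 4). They do not fall into category 0 either, because Ab is Yes.

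**Rules corrected to the table's own ranking.** Category 7 becomes Ab Yes with I, Ac and C No: P free, 2 patterns. Category 8 becomes I Yes with Ac and C No: P and Ab free, 4 patterns. The total is 1 + 1 + 2 + 4 + 8 + 16 = 32, with no pattern unclassified and none classified twice.

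**Sensitivity to the None wording.** If the four questions are taken to be those of categories 7 to 10, a preparatory-only pattern meets both 6 and 0, and the double-coded count becomes 2 + 1 = 3. The 4 unclassified patterns and the empty category 7 are unchanged.

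**The case against.** The best defense is that this is a slip in item names with limited consequences. The labels, the numbering and the sound rules for 6, 9 and 10 show what was intended, and section 14 says programs are checked for their logic. The outputs are descriptive and no hypothesis test rests on them.

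The double coding is also largely handled elsewhere. The combined variable takes the highest score at the visit and the Parts I and III shift table takes the worst category, so both resolve an 8/9 overlap to 9.

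Nor does an affected child vanish from every table. The combined score still takes the ideation score, and the worst category over Parts I and III draws on other visits. Visit data are listed (section 6.1), and a suicide/self-injury SMQ summary is planned (section 9.4).

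Much of this stands, and it narrows the consequences. The overlap stays open only in the by-visit behavior frequencies, for which no highest-score rule is stated. In the combined variable and the shift table the effect is under-classification, not certain loss. The 4 of 32 is a count of patterns and says nothing about how often they occur.

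None of it restores the aborted attempts. A highest-score rule cannot recover a score that was never assigned. Listings and the SMQ do not correct the C-SSRS tables, and the SMQ helps only if the event was also reported as an adverse event. A programmer who quietly repaired the rule would produce output that departs from the SAP.

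**Conclusion.** The concern holds, and it must be fixed. As written, category 7 has no possible members, 4 of 32 response patterns receive no category, and 2 meet both category 8 and category 9 (3 under a narrower reading of the None rule). Nothing else in the SAP supplies a correct derivation.

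The certain loss is in the behavior category itself. In the combined variable, assuming an unassigned behavior score is treated as missing, the child falls back to the ideation score at that visit, which may be 0 and would then read as no suicidal ideation or behavior. The conclusion assumes the rules are programmed literally. How many children would be affected cannot be told from the document and may be small.

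**What to change.** Reword the behavior rules in section 9.13:

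- Category 7: Aborted Attempt Yes; Interrupted Attempt, Actual Attempt and Completed Suicide all No.
- Category 8: Interrupted Attempt Yes; Actual Attempt and Completed Suicide both No.
- Category 0: all five behavior items No.

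Equivalently, state once that the behavior category is the highest-ranked item answered Yes and 0 if none is. State also that this single category is the one used in the by-visit behavior frequencies. The cost is a few words of SAP text and one derivation, applied before the interim and final C-SSRS outputs are produced. It needs no additional data and has no downside.

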10.1. Endpoints

The endpoints that will be included in the interim analysis include:

Safety Endpoints:

The following safety endpoints will be assessed in Part I (up to and including Week 28 visit):

- The incidence of adverse events
- The observed values and the changes from baseline in vital signs
- The observed values and the changes from baseline in the Children's Depression Inventory, Second Edition, Parent and Self-Report Profiles (CDI-2)
- The observed values in the Children's Columbia-Suicide Severity Rating Scale (C-SSRS)
- The observed values in electrocardiogram (ECG) parameters and the shifts from parent study baseline for clinically significant abnormal findings
- The observed values and the changes from baseline in clinical laboratory parameters (hematology, serum chemistry, and urinalysis)

Exploratory Efficacy Endpoints:

The following exploratory endpoints will be assessed in Part I at the visits in which the data is collected (up to and including Week 28 visit):

- [REDACTED]
- [REDACTED]
- [REDACTED]
- [REDACTED]
- [REDACTED]
- [REDACTED]
- [REDACTED]
- [REDACTED]
- [REDACTED]
- [REDACTED]
- [REDACTED]
- [REDACTED]
- [REDACTED]
- [REDACTED]
- [REDACTED]

This document is confidential.

[REDACTED]

[REDACTED]

[REDACTED]

[REDACTED]

[REDACTED]

[REDACTED]

[REDACTED]

[REDACTED]

10.2. Demographic, Other Baseline Characteristics and Prior Medication

Demographic, other baseline characteristics and medication included with interim will include:

- Disposition for Part I as described in Section 7.1. Only Part I will be included;
- Demographics and other baseline characteristics for the ITT and Safety Analysis Set (Section 7.2);
- Medical History for the Safety Analysis Set (Section 7.3);
- Prior Medication for Safety Analysis Set (Section 7.4).

10.3. Safety

All safety endpoints will be presented similarly to Section 9. TEAE occurred in Part I and resolved in Part II or Part III will be included and will be considered as ongoing.

10.4. Efficacy

All efficacy endpoint will be presented similarly to Section 8.2.4 and Section 8.2.5.

All efficacy endpoints are exploratory. Only assessments until Week 28 will be included.

11. Changes from Analysis Planned in Protocol

Summary based on the ITT Analysis Set will include one column for all patients. In protocol, analyses based on the ITT Analysis Set are by randomized treatment and “Not Randomized” for patients not entered Part II (Protocol Section 9.2.1).

Prior ADHD and antidepressant medications, change in ADHD medications and symptoms are added.

Two efficacy exploratory endpoints are added to Part II:

[REDACTED]

[REDACTED]

Additional exploratory endpoints are added to Parts I and III combined:

[REDACTED]

This document is confidential.

Statistical Analysis Plan for Interventional Studies

Sponsor: Teva Branded Pharmaceutical Products R&D, Inc./Nuvelution TS Pharma, INC.

Protocol No.: TV50717-CNS-30047

█ [REDACTED]

█ [REDACTED]

█ [REDACTED]

This document is confidential.

12. Reference List

[Redacted Reference List Content]

This document is confidential.

13. Programming Considerations

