3.7. Administration of Study Medication

During the open-label periods (Parts I and Part III open-label maintenance period), TEV-50717 tablets are available in the following dose strengths: 6, 9, and 12 mg. Patients will receive twice daily dosing for up to 54 weeks (those on the 6-mg dose will receive once-daily dosing), with an initial 7-week titration period to allow for optimal dose selection.

During the randomized drug withdrawal period (Part II) and re-titration period of Part III, TEV-50717 tablets are available in the following dose strengths: 6, 9, 12, 15, and 18 mg, all of which are identical in size, shape, and color (white). The IMP will be supplied in 20-count bottles. The placebo tablets and packaging will match those for TEV-50717.

Patients who receive TEV-50717 during the randomized drug withdrawal period (Part II) will remain on their maintenance dose of blinded active IMP during Part III of the study, and those assigned to placebo during the randomized drug withdrawal period (Part II) will undergo blinded re-titration from the start of week 31 to the start of week 34 back to their previously established maintenance dose from the end of week 28. Note that, because IMP is dispensed for 2-week periods, patients will use blinded bottles through the end of week 34; however, all patients should be on active treatment at the start of week 31.

IMP will be administered as oral tablets at a starting dose of 6 mg once daily. Titration schemes during part I are based on body weight on day 1 and the maximum daily dose is determined by body weight and cytochrome P450 2D6 (CYP2D6) impairment status on day 1. Titration during Part III is based on the previously established maintenance dose in Part I. Refer to protocol Section 5.1 for additional details.

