6.2.7. Periods Start and End Dates

Adverse events will also be summarized by periods below:

- Part I Titration Period
 - Start Date - the Day 1 visit;
 - End Date - the last dose of study treatment during titration period (up to and including Week 8 visit).
- Part I Maintenance Period

For patients who completed any assessments after Week 8 visit, the start and end dates are:

 - Start Date - the day after Week 8 visit;
 - End Date - the Part I last dose date .
- Part II and III Treatment Period

For patients who are randomized

 - Start Date - the start date of Part II;
 - End Date - the last dose of study treatment during the study.
- Follow-up Period
 - Start Date - the day after the last dose of study treatment;
 - End Date - the day of the last visit.

Periods are not corresponding to Parts. Events occurred after last dose of study treatment are included with each Parts, but are not included period. Events after the last dose of study treatment will all be summarized with the follow-up period.

This document is confidential.

Statistical Analysis Plan for Interventional Studies

Sponsor: Teva Branded Pharmaceutical Products R&D, Inc./Nuvelution TS Pharma, INC.
 Protocol No.: TV50717-CNS-30047

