7.4.2. Other Therapies

Prior non-pharmacological treatment will be collected in the CRF. Type of treatment/procedure and indication will be summarized.

Prior pharmacological treatment given for TS will be summarized. Table will include number of patients with previous treatment given for TS, total duration of treatment, and best response to treatment. For an ongoing treatment, date of informed consent will be used to compute duration.

Prior non-pharmacological treatments will be listed.

This document is confidential.

8. Efficacy

All assessments in the Parts I and III combined are exploratory in nature and no inferential statistics will be applied; however, inferential statistics will be applied to the efficacy endpoint in the Part II. In general, all efficacy endpoints will be included in the efficacy analyses for the Parts I and III combined based on ITT Analysis Set. Summary for the Parts I and III combined will include one column for all patients and will not include the assessments during Part II. Efficacy endpoints that are assessed in both Parts I and III and in Part II will be presented in two sets of the tables: one for Parts I and III combined, and one for Part II.

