8.2.4. The Analysis of the Change Scores in Parts I and III Combined

These change scores are included as the exploratory endpoints for Parts I and III combined: the change in the TS-CGI score, the TS-PGII score, the C&A-GTS QOL ADL subscale score, the TTS of the YGTSS, the TS-PGIS score, the YGTSS impairment score, the MTSS of the YGTSS, the VTSS of the YGTSS, the GSS of the YGTSS, VAS in the C&A-GTS QOL score, CY-BOCS scores, and the C&A-GTS QOL total

This document is confidential.

Statistical Analysis Plan for Interventional Studies

Sponsor: Teva Branded Pharmaceutical Products R&D, Inc./Nuvelution TS Pharma, INC.
Protocol No.: TV50717-CNS-30047

and subscale score, tic-free score, the percent change in the TTS of the YGTSS from baseline to each visit.

These changes will be derived as the assessment value minus baseline. The observed values and the changes from baseline will be summarized at each visit in which the scale is administered, including Week 28, but not Week 30 visit if assessed. The summary will be based on the ITT Analysis Set.

8.2.5. Proportion of Patients with Improvement on the TTS of the YGTSS and TS-CGI for Parts I and III Combined

Proportion of patients who have $\geq 25\%$ reduction, $\geq 35\%$ reduction from baseline on the TTS of the YGTSS to each visit, $\geq 25\%$ reduction from baseline of the parent study to each visit, a reduction of ≥ 1 point in the TS-CGI score from baseline to each visit will be analyzed. Frequency, and proportion will be presented at each visit for the ITT Analysis Set in the Parts I and III combined. Summary tables will include one column for all patients. All visits, including Week 28, will be included, but not Week 30.

This document is confidential.

9. Safety

For by-visit safety endpoints, e.g. vital sign, CDI-2, summaries will be presented for:

- The observed values and the change from baseline. The change will be derived as the observed value at the specific visit minus the baseline. Week 30 assessments will not be included. Analyses will be based on the Safety Analysis Set with an overall column.
- The observed values and the change from Week 28 to Week 30. The change will be derived as the observed value at Week 30 minus the randomized withdrawal baseline. Tables will be based on the RWSAF population and presented by actual treatment received during randomized drug withdrawal period and overall. This will only be included if assessment is performed at Week 30 visit.

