- Parts I and III combined, based on the Safety Analysis Set. The events that occurred in Part II will not be included. Table will contain one overall column. All tables will include number, frequency of patients with the event, and EAIR. All AE tables will be prepared for Part I and III combined.

This document is confidential.

Statistical Analysis Plan for Interventional Studies

Sponsor: Teva Branded Pharmaceutical Products R&D, Inc./Nuvelution TS Pharma, INC.
Protocol No.: TV50717-CNS-30047

- Part II is based on the RWSAF population and presented by the actual treatment received during the randomized withdrawal period. Table will include number and frequency of patients with the event. All AE tables will be prepared for Part II.
- Parts I, II, and III combined, based on the Safety Analysis Set. Table will contain one overall column. The Parts I, II, and III combined tables will be presented for entire study and by each Part. All tables will include number, frequency, and the EAIR. The overview of AEs, AEs by SOC and preferred terms, and the SMQ summaries will be presented for Parts I, II, and III combined.
- Periods, based on the Safety Analysis Set. Table will contain one overall column. All tables will include number, frequency, and the EAIR. The overview of AEs and AEs by SOC and preferred terms will be presented by periods.

For summary of patient, the following rules will apply:

1. Patients having more than 1 event with the same PT will be counted once for that term.
2. Patients having more than 1 event with the same SOC will be counted once for each event and once for that SOC.
3. For tabulations by severity, only a patient's most severe event within the category (e.g. overall, SOC, PT) will be counted; similarly, for tabulations by relationship, only a patient's most related event within a category will be counted. The denominator for percentages will be the number of patients in Safety Analysis Set for the given treatment group or overall (i.e., the N's for the columns).

For the summary of incidence rate, all events will be included.

Listings will be provided for all AEs and the following subsets:

- All TEAEs
- Serious TEAEs
- TEAEs leading to study drug discontinuation
- TEAEs leading to dose interruption
- TEAEs leading to dose reduction
- TEAEs leading to death.

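### Part III is reported in one column, so Week 34 results and early Part III adverse events pool continued TEV-50717 with restart after placebo

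*SAP*

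**What the plan says.** Section 11 of the SAP lists this as a change from the protocol: "Summary based on the ITT Analysis Set will include one column for all patients". It records that in the protocol "analyses based on the ITT Analysis Set are by randomized treatment", with a further Not Randomized group for patients who did not enter Part II. No reason is given for the change.

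The opening of Section 8 applies the same layout to efficacy: "Summary for the Parts I and III combined will include one column for all patients and will not include the assessments during Part II". Section 8.2.5 repeats it for the responder proportions. For by-visit safety in Parts I and III, Section 9 says "Analyses will be based on the Safety Analysis Set with an overall column". For adverse events in Parts I and III combined, Section 9.4 says "The events that occurred in Part II will not be included. Table will contain one overall column". The tables by Part and by Period in Section 9.4 also have one overall column.

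Section 3.7 describes how Part III begins. Patients who had TEV-50717 in Part II stay on their maintenance dose. Those who had placebo "will undergo blinded re-titration from the start of week 31 to the start of week 34". Section 6.2.7 then defines a single on-treatment adverse event period after Week 28, the "Part II and III Treatment Period", running from the start of Part II to the last dose.

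**The concern.** The second and third parts of this study follow from a 2:1 randomization, so the patients who reach Week 34 have two different recent histories. One group has been treated without interruption. The other has had two weeks of placebo and three weeks of re-titration. A single column averages them.

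For efficacy, tics that have not fully recovered in the former placebo group would make the Week 34 mean look like some loss of effect on continued treatment. Their later recovery would look like further improvement. These descriptive tables are the SAP's only post-withdrawal evidence on its long-term efficacy objective (Section 3.2).

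For safety, no summary table separates adverse events during re-titration from those on uninterrupted treatment. The period in Section 6.2.7 also counts placebo time as treatment exposure.

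Some information is lost as well. By Table 3, TS-CGI, TS-PGII, TS-PGIS, Tic-free Interval, CY-BOCS and C&A-GTS-QOL are not done at Week 30. Week 34 is therefore their first value after randomization, and it is shown without the arm.

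**Working it through.** **Inputs.** Allocation 2:1 TEV-50717 to placebo (Sections 3.5 and 3.6). Planning difference 4.5 TTS points, SD 9.0, type 1 error 5% (Section 3.5), two-sided (Section 6.1). Re-titration from the start of Week 31 to the start of Week 34 (Section 3.7). Week 34 visit on Day 238 ±3 (Table 3).

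**The plan's own figures.** Section 3.5 gives 90% power with at least 190 patients and below 50% at 70 or fewer. With n1 = N/3 and n2 = 2N/3, the standardized difference is 4.5 / (9.0 × √(1/n1 + 1/n2)).
- N = 190: 4.5 / (9.0 × 0.1539) = 3.249. Power = Φ(3.249 − 1.960) = 90.1% (89.8% with the noncentral t).
- N = 70: 4.5 / (9.0 × 0.2536) = 1.972. Power = Φ(1.972 − 1.960) = 50.5% (49.4% with the noncentral t).

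Both agree with the SAP. The present point does not depend on power. The check only confirms how the 4.5, the 9.0 and the 2:1 ratio are meant.

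**Share re-titrated.** 1 / (2 + 1) = 33.3% of randomized patients.

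**Time back at maintenance dose by Week 34.** Week 33 ends on Day 231 and the Week 34 visit is on Day 238, so about 7 days, or 4 to 10 with the ±3-day window.

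**Shift in the pooled Week 34 mean among randomized patients.** Shift = (1/3) × residual difference between arms = (1/3) × 4.5 × f = 1.5f, where f is the fraction of the withdrawal effect not yet regained. The SAP gives no value for f, so it is assumed:

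| f | Residual difference | Shift in pooled mean |
|---|---|---|
| 0 | 0 | 0 |
| 0.5 | 2.25 | 0.75 |
| 1 | 4.5 | 1.5 |

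**Visit windows.** Section 6.4 maps unscheduled and early termination YGTSS assessments, from the day after the Week 30 visit to Day 262, to Week 34. An early termination value is used when there is no scheduled one. A former placebo patient who leaves during re-titration can therefore supply a Week 34 value with little or no time back at dose.

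**Adverse event time.** Take patients treated to the end of Week 54.
- Part III treatment lasts 24 weeks (31-54). Re-titration takes 3 of them in one third of patients: (1/3) × 3/24 = 4.2% of Part III treatment time.
- The Section 6.2.7 period lasts 26 weeks (29-54). Placebo takes 2 of them in one third of patients: (1/3) × 2/26 = 2.6% of the time in that period.

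These are shares of time, not of events. Exposure is also cut at the first event (Section 6.2.8), so the early weeks can weigh somewhat more in the rates.

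**By-visit safety.** Vital signs are taken at Week 32 (Table 3), inside re-titration, and go into the same overall column.

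**The case against.** The strongest reply is that this is a disclosed choice about descriptive tables. Section 8 says that no inferential statistics apply to Parts I and III. Maintenance of effect is tested in Part II by arm, and the Week 28 value before withdrawal appears in the combined tables. All of that stands. A reader might infer that a test or its error rate is compromised, but none is.

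Three other stronger readings are tempting and are not supported.
- **That the whole Week 34-54 course is distorted.** All patients should be on active drug from the start of Week 31 and back at their dose by the start of Week 34. The documents support carry-over mainly at Week 34, and nothing shows it at Week 41 or 54.
- **That the SAP departs from the protocol for safety as well.** Section 11 speaks only of ITT summaries. Splitting the safety tables would be an addition, not a restoration.
- **That withdrawal-period adverse events cannot be isolated.** Section 9.4 shows Part II by actual treatment and shows events by Part, Section 6.2.7 has a separate Follow-up Period, and listings are sorted by treatment group. What remains is that, within Part III, re-titration is not tabulated apart from maintenance, and that the combined Part II and III period pools placebo time.

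The size is also open to challenge. The 4.5 points is a planning value for Part II, whose primary population is limited to responders (Section 5.6), so applying it to all randomized patients is an assumption. The maximum of 1.5 points is 1.5/9.0 = 0.17 of the planning SD and requires no recovery at all. That is fair. But f cannot be known in advance, and the single column would hide it.

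**Conclusion.** The point holds as a weakness in presentation. The SAP drops the protocol's ITT split without a reason and shows no Part III table by Part II arm. As a result, Week 34 results and Weeks 31-33 adverse events pool two treatment conditions in about a 2:1 mix. The pooled Week 34 TTS mean would move by between 0 and 1.5 points, provided that the 4.5-point planning difference applies to all randomized patients and that f lies between 0 and 1. The effect should be largest at Week 34 and in Weeks 31-33, and may be negligible by Weeks 41-54. Re-titration and placebo time are small shares of the exposure in which they are pooled (4.2% and 2.6% for patients treated to Week 54). The tested Part II comparison is untouched. The change is worth making because it is cheap and these tables are meant to describe long-term treatment.

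**What to change.** 1. Keep the Total column and add Part II TEV-50717 and Part II placebo columns for visits after Week 30 in Sections 8.2.4 and 8.2.5 and in the by-visit safety tables, and for the Part III adverse event and EAIR tables. A Not Randomized column is not needed after Week 30, because randomization precedes Part III and the column would be essentially empty.
2. In Section 6.2.7, replace the combined period with Part II (shown by actual treatment, so that placebo time is not pooled as treatment exposure), the blinded re-titration weeks, and Part III maintenance.
3. State that the Week 34 total will be read together with the by-arm columns. Long-term statements should not rest on the TEV-50717 column alone, since that would set aside about a third of the randomized patients.

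The cost is more columns with smaller numbers. If all 157 patients enrolled by 09Aug2019 were randomized, the columns would hold about 105 and 52. With 100 randomized they would hold about 67 and 33. No new data are needed. Assignments are available after database lock, so blinding is not affected.
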